10.5. Physical Examinations

Physical examinations are conducted at baseline. A by subject listing will be completed to display all baseline physical examination information, as well as any optional PE information collected.

10.6. Other Safety Measures

C-SSRS results will be presented in subject data listings.

USP summary scores (stress urinary incontinence score, overactive bladder score, and low stream score) will be summarized descriptively by time point for the observed value as well as for the change from baseline value. All USP data (including the 10 individual questions) will be presented in listings.

ECG parameters will be summarized descriptively by time point for the observed value as well as for the change from baseline value. All ECG data will be presented in listings.

No other safety analyses have been prospectively defined. If, however, after study results are reviewed, or the DSMB or Sponsor recommend additional safety parameters or analyses be completed, they will be fully described and documented in the final clinical study report. The SAP does not need to be amended to complete any other safety measures identified as post-hoc.

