11.5 Safety Endpoints

Safety endpoints will be reported on the Safety population. Subjects will be reported according to the treatment they actually received. Safety assessment will be based on descriptive statistics and individual subject listings. No statistical tests will be performed for any of the safety assessments.

All reported AEs will be mapped to the Medical Dictionary for Regulatory Activities (MedDRA) system organ classifications (SOCs) and preferred terms (PTs). If a subject reports multiple events of a single PT, the greatest severity and strongest investigator assessment of relationship to study treatment will be assigned to that PT. Should an event have a missing severity or relationship, it will be classified as having the highest severity and/or strongest relationship to study drug. Summaries of treatment-emergent AEs (TEAEs) will include any AEs reported beginning with the first dose of study treatment on Day 1. The occurrence of TEAEs will be summarized by treatment group using SOCs, PTs, and severity. Separate summaries of treatment-emergent SAEs, TEAEs considered related to study treatment, and events leading to the discontinuation of study drug will be generated.

Descriptive summaries of vital signs, clinical laboratory results, USP results, and the C-SSRS results will be presented by study visit and treatment group. The number and percentage of subjects with treatment-emergent clinical laboratory abnormalities will be summarized by treatment group. Normal range clinical laboratory shifts from baseline to end of study will be summarized by treatment group.

Concomitant medications will be coded using the World Health Organization (WHO) dictionary. These data will be summarized by treatment group. Previous and concomitant medications will be presented in a data listing.

Subject disposition will be presented for all subjects. The numbers of subjects who complete the study and who discontinue early from the study will be provided. The reasons for early discontinuation will also be presented.

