3.3. Summary of Statistical Analysis Changes to the Protocol

The analyses described in this analysis plan are consistent with the analyses described in the study protocol.

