10.3. Clinical Laboratory Evaluations

Clinical Laboratory results will be summarized descriptively by time point for the observed value as well as for the change from baseline value. In addition, laboratory shift tables will be provided for all laboratory parameters where low/normal/high or abnormal/normal status can be ascertained. Listings of individual laboratory parameters by visit with normal ranges and abnormality assessments will also be completed by subject.

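### The SAP omits two safety summaries that Protocol 11.5 commits to (C-SSRS by visit, and subjects with treatment-emergent laboratory abnormalities) while declaring no departure from the protocol

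*SAP*

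**What the plan says.** Protocol 11.5 sets out three outputs that matter here, each in its own sentence or clause:

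- C-SSRS, together with vital signs, laboratory results and USP: "Descriptive summaries of vital signs, clinical laboratory results, USP results, and the C-SSRS results will be presented by study visit and treatment group".
- Laboratory abnormalities: "The number and percentage of subjects with treatment-emergent clinical laboratory abnormalities will be summarized by treatment group".
- Laboratory shifts: "Normal range clinical laboratory shifts from baseline to end of study will be summarized by treatment group".

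The SAP treats them as follows:

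- SAP 10.6, on C-SSRS: "C-SSRS results will be presented in subject data listings". Nothing else is planned for the instrument, and the section ends its list of analyses with "No other safety analyses have been prospectively defined".
- SAP 10.3, on laboratory data: "Clinical Laboratory results will be summarized descriptively by time point for the observed value as well as for the change from baseline value", then "In addition, laboratory shift tables will be provided for all laboratory parameters where low/normal/high or abnormal/normal status can be ascertained". By-subject listings with normal ranges and abnormality assessments are added.
- SAP 3.3, on departures: "The analyses described in this analysis plan are consistent with the analyses described in the study protocol".

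SAP 4.2.1 lists C-SSRS among the safety endpoints, and SAP 5.3 lists it among the variables to be analysed. The revision history (SAP 12) mentions neither a C-SSRS change nor a laboratory change.

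**The concern.** Long-term safety and tolerability is the primary objective, and the study exists largely to supply data at 80 mg/day (Protocol 11.3). For such a study the safety tables are the main result. A protocol commitment to tabulate a safety measure should either reach the SAP or be withdrawn openly. Here two commitments disappear and the section meant to record departures says there are none.

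The practical stake is pre-specification. SAP 7.4.1 presents tables by modal dose (40, 60 and 80 mg, and overall). A measure with no planned table has no pre-specified result at 80 mg. If a table is wanted later, its categories, time window and denominator would be chosen after the data have been seen.

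**Working it through.** The plan gives no figure to reproduce. The check is a comparison of the two documents, followed by two short counts.

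**1. Outputs side by side**

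| Protocol 11.5 output | SAP counterpart | Carried over |
|---|---|---|
| C-SSRS summary by visit | 10.6: listings only | No |
| n (%) with treatment-emergent laboratory abnormality | None in 10.3; treatment-emergent is defined only for adverse events (10.1) | No |
| Laboratory shifts from baseline | 10.3: shift tables | Yes |

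Of three outputs, one is carried over and 3 − 1 = 2 are not.

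**2. Does another SAP clause restore them?** SAP 7.4.1 promises descriptive summaries where appropriate, but the same section keeps data without a planned analysis out of tables and figures. Within SAP 10.6, USP and ECG each receive summaries by time point as well as listings. C-SSRS receives listings alone. The specific rule is clear and the general clause does not override it.

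**3. Does the protocol version explain it?** The SAP cites Amendment 1, and the protocol supplied includes US Amendment 2. The Amendment 2 change log lists no change to Section 11.5, so version lag does not appear to be the cause. The Amendment 1 text is not available to confirm this.

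**4. How many C-SSRS assessments are affected?** Protocol Table 1 schedules C-SSRS after baseline at Visits 1 to 6 and Visit 8, so 6 + 1 = 7. Visit 7 is a telephone contact for adverse events and concomitant medication (Protocol 6.5). With the planned enrolment of approximately 300, 7 × 300 = 2,100. This is a ceiling: it assumes that every subject attends every visit, and Protocol 5 allows the sponsor to stop enrolment sooner.

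**5. What do the shift tables supply?** SAP 7.3.1 assigns unscheduled tests to the nearest scheduled test and takes the most conservative result at that time point, which implies shift tables by time point. Laboratory samples after baseline are due at Visits 2 to 6 and Visit 8 (Protocol 6.3, 6.4, 6.6). The taper ends at Week 56 and Visit 8 is at Week 60, which is 60 − 56 = 4 weeks later. A subject who completes therefore has five scheduled on-treatment samples (Visits 2, 3, 4, 5 and 6). Suppose a parameter shows k subjects moving from normal to high at each of the five visits:

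- if they are the same subjects each time, k subjects were ever abnormal;
- if they are different subjects each time, 5k were (while 5k does not exceed the number normal at baseline).

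The tables fit any value from k to 5k. If the shift is instead from baseline to end of study, as in Protocol 11.5, a completer contributes only the Week 60 value, and an abnormality that had resolved by then would not show. Neither form gives the promised count.

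**The case against.** The strongest case on the other side concerns the laboratory half, and much of it stands.

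- SAP 10.3 does analyse the laboratory endpoint: observed values, changes, shift tables and listings. Shift tables are counts of subjects, so each time point has numerators and denominators per parameter. What is missing is the any-time count and its definition. Protocol 11.5 does not define the term either.
- Under Protocol 9.5, a clinically significant abnormality that requires treatment or leads to discontinuation must be classified as an adverse event. Those with onset or worsening on treatment would reach the TEAE tables.
- C-SSRS findings are not lost. All collected data are listed. Exclusion criterion 7 excludes subjects who answer yes to question 1 or 2 at baseline, so ideation recorded later would generally be new and could be counted from the listing.
- The study is single-arm and descriptive with no tests, and SAP 10.6 allows further safety analyses without amending the SAP.

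These points reduce the consequence but do not remove the conflict. The protocol lists the laboratory count and the shifts as separate outputs. A count made from listings, or added under the SAP 10.6 allowance, is post hoc. Nothing in the objection reconciles the C-SSRS rule with Protocol 11.5 or makes the statement in SAP 3.3 correct.

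**Conclusion.** The point holds as an undeclared departure from the protocol on the primary, safety, objective. The C-SSRS omission is unambiguous and also sits badly with SAP 4.2.1 and 5.3. The laboratory omission is narrower: one any-time count per parameter, with its definition. In size, the report would contain no pre-specified C-SSRS table by visit or modal dose, covering at most about 2,100 post-baseline assessments, and no pre-specified any-time incidence of laboratory abnormality. The first figure rests on full enrolment and full attendance. The second rests on reading the shift tables as by time point or to end of study. A worst-value-ever shift table would come close to the missing count, but the SAP does not describe one.

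Three stronger readings are tempting and are not supported:

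- A reader might infer that these endpoints would have no numerator or denominator, or that the rates could not be known. The shift tables and complete listings show otherwise.
- A reader might infer that a planned comparison with the double-blind Study OS440-3004 is lost. Neither document plans a safety comparison with that study for these measures or describes that study's C-SSRS or laboratory tables.
- A reader might infer a loss of statistical precision. With zero events in 300 subjects the one-sided 95% upper bound is 1 − 0.05^(1/300) = 0.99%, whether the results are tabulated or listed. The documents plan no such bounds.

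**What to change.** - **SAP 10.6:** add a table of n (%) of subjects with post-baseline suicidal ideation or behaviour, by visit and overall, by modal dose. State whether the overall row includes Visit 8, which falls after the last dose for subjects who complete.
- **SAP 10.3:** add, per parameter and by modal dose, the n (%) of subjects with a treatment-emergent abnormality at any time. Define it as new or worsened relative to baseline, in the same window as TEAEs (first dose to last dose, SAP 10.1). A definition limited to subjects normal at baseline would miss worsening from an abnormal baseline. The SAP should also say what counts as worsening there, because a low/normal/high flag alone cannot show a value moving further out of range.
- **SAP 3.3:** correct the statement, or declare and justify any departure that is kept.

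The cost is two tables and a few lines of text. No new data are needed. The SAP has already been revised twice, including to add adverse event analyses and an exposure table, so a further revision of this kind is routine. It should be made before database lock so that both tables count as pre-specified.

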4.2. Study Endpoints

4.2.1. Safety Endpoints

Safety endpoints include the following:

- Adverse events
- Vital signs
- Clinical laboratory tests
- 12-lead electrocardiograms (ECGs)
- Urinary Symptom Profile - USP© questionnaire (USP)
- Columbia-Suicide Severity Rating Scale (C-SSRS)

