5.3. Analysis Variables

Variables to be analyzed include demographics and baseline characteristics, safety variables (adverse events, vital signs, clinical laboratory investigations, ECGs, USP questionnaire, and C-SSRS), and efficacy variables (PGIC, TNmAS-MAL, TNmAS-TL, and EDSS). See Section 8 of the protocol for further details on the efficacy variables. Derived variables from study endpoints are described with the sections describing the analyses for these endpoints.

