7.4. Planned Study Analyses

7.4.1. Statistical Summaries: Descriptive and Inferential

No statistical tests will be performed in this study.

Descriptive summaries of variables will be provided where appropriate. For continuous variables, the number of non-missing values (n) and the median, mean, standard deviation, minimum, and maximum will be tabulated. For categorical variables, the counts and proportions of each value will be tabulated. Expansion of descriptive table categories may occur if such elaborations are thought to be useful.

For the summary statistics of all numerical variables unless otherwise specified, minimum and maximum will be displayed to the same level of precision as reported. Mean and median will be displayed to one level of precision greater than the data collected. The standard deviation / standard error will be displayed to two levels of precision greater than the data collected.

Change from baseline scores will be calculated as the post-baseline measurement minus the baseline value.

Unless otherwise specified, all tables will be presented by Modal Dose of 40 mg, 60 mg, 80 mg, and Overall group.

All collected data will be presented in listings. Data not subject to analysis according to this plan will not appear in any tables or figures but will be included in the data listings.

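### SAP 10.6 puts the C-SSRS in listings only, although Protocol 11.5 plans summaries by visit and SAP 3.3 declares no departure from the protocol

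*SAP*

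**What the plan says.** Protocol 11.5 gives the commitment: "Descriptive summaries of vital signs, clinical laboratory results, USP results, and the C-SSRS results will be presented by study visit and treatment group". Protocol Table 1 schedules the C-SSRS at every clinic visit, and Protocol 9.6.3 refers to that schedule.

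The SAP takes the endpoint over. Its list of safety endpoints in 4.2.1 includes "Columbia-Suicide Severity Rating Scale (C-SSRS"), and 5.3 names, among the variables for analysis, "safety variables (adverse events, vital signs, clinical laboratory investigations, ECGs, USP questionnaire, and C-SSRS").

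Where the SAP describes the output, in 10.6, the text is "C-SSRS results will be presented in subject data listings". The same section gives the USP and the ECG descriptive summaries by time point, and adds that no further safety analysis is planned in advance. SAP 7.4.1 states that "Data not subject to analysis according to this plan will not appear in any tables or figures".

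SAP 3.3 says: "The analyses described in this analysis plan are consistent with the analyses described in the study protocol". The revision history in SAP section 12 covers the TEAE window, extra adverse event tables, a second Ashworth baseline, exposure and the modal dose categories. It does not mention the C-SSRS.

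**The concern.** The SAP drops an analysis that the protocol promises, does not say so, and states that nothing has changed. It also contradicts itself, because an endpoint marked for analysis has no analysis attached to it.

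At stake is how suicidality is reported in a study whose primary objective is long-term safety and tolerability. Under the SAP as written, a reader of the study report who wants the proportion of subjects with ideation or behaviour at any visit must count it from subject listings and choose the denominator. If the sponsor adds a table once the results have been reviewed, that table is post hoc under the SAP's own terms: "The SAP does not need to be amended to complete any other safety measures identified as post-hoc". A prespecified table avoids this at almost no cost.

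**Working it through.** No error rate, power or sample size figure is involved. The check compares texts and adds some simple counting.

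**1. Output planned for each safety endpoint in SAP 4.2.1.**

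| Endpoint | SAP section | Table planned |
|---|---|---|
| Adverse events | 10.1 to 10.2.3 | Yes |
| Clinical laboratory tests | 10.3 | Yes |
| Vital signs | 10.4 | Yes |
| 12-lead ECG | 10.6 | Yes |
| USP questionnaire | 10.6 | Yes |
| C-SSRS | 10.6 | No, listing only |

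Tabulated: 6 − 1 = 5 of 6.

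**2. Against the protocol sentence.** Protocol 11.5 names four measures for summary by visit: vital signs, laboratory results, USP and C-SSRS. The SAP summarises the first three by time point and omits the fourth. It does summarise the ECG, which that sentence does not name.

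**3. Whether general SAP text restores the table.** SAP 7.4.1 offers descriptive summaries where they are appropriate. That is a general permission, whereas 10.6 is specific to the C-SSRS and names listings. Section 10.6 then closes the list of planned safety analyses, and 7.4.1 keeps unanalysed data out of tables. No other SAP section plans a C-SSRS table.

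**4. Whether the protocol version explains it.** SAP 3.1 cites the Amendment 1 protocol; the protocol supplied is US Amendment 2. The Appendix 8 change lists for both amendments show no specific change to section 11.5, so on that record the version gap does not account for the difference.

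**5. What reaches a table by another route.** A suicidal event recorded as an adverse event, with onset or worsening between first and last dose, enters the TEAE tables (SAP 10.1). If serious, it also enters the TESAE table and has a narrative (10.2.2). If it stops or interrupts study drug, it enters that table (10.2.3). Deaths have narratives (10.2.1). This route depends on the site recording an adverse event. Protocol 9.6.2 makes a 4-point rise in the USP score an adverse event; Protocol 9.6.3 has no corresponding rule for the C-SSRS.

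**6. Recall interval, which governs how a table can be built.** Post-baseline C-SSRS visits in Protocol Table 1 are Weeks 2, 6, 14, 28, 42, 54 and 60, seven in all. Intervals between consecutive visits: 6 − 2 = 4, 14 − 6 = 8, 28 − 14 = 14, 42 − 28 = 14, 54 − 42 = 12 and 60 − 54 = 6 weeks. Appendix 4 includes a form that asks about the time since the last visit, so one answer can cover 14 weeks on the planned schedule. A subject who withdraws early tapers over two weeks and also owes the Visit 8 assessments. If those follow the last dose, the answer can still reach back into time on drug.

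**The case against.** The best defence has four parts.

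*Nothing is lost.* This stands. All C-SSRS results are listed, and the adverse event tables and narratives in step 5 remain. A reader might infer that suicidality will go unreported; the documents do not support that. What is missing is a prespecified summary of the instrument.

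*The study is single-arm and has no tests, so a listing is enough.* The first half is true. But the protocol promised a descriptive summary, which needs no comparator. A single-arm study has no treatment groups in the ordinary sense, yet SAP 7.4.1 already supplies columns: "all tables will be presented by Modal Dose of 40 mg, 60 mg, 80 mg, and Overall group". The commitment to report by visit is unaffected.

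*The protocol prevails.* SAP 5.1 calls the protocol the definitive reference, though in a section that summarises the study design, so its reach is arguable. If it does apply here, the table is owed and SAP 10.6 needs correcting.

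*A table could mislead.* This stands as a constraint on the fix. A reader might want events split into on-drug and off-drug by comparing the assessment date with the last dose date. Step 6 shows that this would place some on-drug events of early withdrawers in the off-drug group. A fixed statement of what the Week 60 answer covers is also unsafe, because Protocol 7.1.1 says that subjects who only reach 40 mg per day have no taper phase. A reader might also treat every post-baseline positive answer as new. Exclusion criterion 7 bars a baseline yes to questions 1 or 2 only; it names no behaviour item.

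**Conclusion.** The inconsistency is real and should be corrected. One of six safety endpoints, and one of the four measures that Protocol 11.5 names for summary by visit, has no table, while SAP 3.3 says that the plan matches the protocol.

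Its weight is moderate. The omission removes a prespecified count, denominator and percentage, not data. The documents give no expected rate of ideation or behaviour, so the number of events left out of tables cannot be estimated, and none is claimed. A reader might also infer a deliberate, concealed change. The documents show only that no change was declared, and an oversight fits equally well.

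The conclusion rests on two readings: that the specific wording of SAP 10.6 governs over the general permission in 7.4.1, and that the Appendix 8 change lists are complete for Protocol 11.5.

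**What to change.** In SAP 10.6, add one descriptive C-SSRS table:

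- **Rows:** each scheduled visit, plus any post-baseline assessment.
- **Content:** number and percentage of assessed subjects with suicidal ideation, and with suicidal behaviour, as reported on the since-last-visit form in Protocol Appendix 4. The denominator is the subjects assessed in that row.
- **Columns:** modal dose 40, 60 and 80 mg, and Overall, as in SAP 7.4.1.
- **Early termination:** assign these assessments to visits by the rule in SAP 7.3.3.
- **Footnote:** each answer covers the whole interval since the previous assessment, so an assessment made after the last dose can include time on drug. Do not classify events as on or off drug by assessment date alone.

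Keep the listings. With this table, SAP 3.3 becomes true for this item. If the sponsor intends listings only, SAP 3.3 should declare and justify the departure from Protocol 11.5.

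The cost is one table from data already collected, with no protocol amendment. The drawback is small cells by visit and modal dose, so percentages should be read alongside their counts.

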11 REPORTING CONVENTIONS

The following reporting conventions will be adopted for the presentation of study data. These conventions will enhance the review process and help to standardize presentation with common notations

